6. CLINICAL AND LABORATORY EVALUATIONS

6.1. Schedule of Evaluations

Evaluation	Screen	Day 1 Pre-Entry and Entry	Day 2	Day 3	Day 4
Informed Consent		X			
Documentation of Disease/Disorder	X	X			
Medical/Treatment History	X				X ¹
Clinical Assessment		X	X	X	X ¹
Targeted Physical Exam		X			X ¹
Side Effect Assessment		X	X	X	X ²
Pregnancy Testing		X			
Nutritional Assessment		X			
Seizure Count		X		X	X
Inpatient		Admit: Noon		D/C: Noon	
Continuous EEG		X	X	½ day	
Laboratory Evaluations: Hematology, Chemistry		X	X	X	X
Laboratory Evaluations: Random glucose, Beta-hydroxybutyrate			X AM & PM	X AM & at D/C	
Blood collection to measure C7 ketones ¹		X	X	X	X
Triheptanoin Supplementation			X		

¹Optional: completed only at discretion of PI or sub-Is

²VA Toxicity Scale optional & completed only at discretion of PI or Sub-Is

6.2. Timing of Evaluations

6.2.1. Pre-Entry Evaluations

6.2.1.1. Screening

In order to evaluate subjects' eligibility to participate prior to traveling to Dallas, a waiver of HIPAA Authorization will be obtained only for the purposes of obtaining information regarding age, diagnosis, height, weight, current dietary therapy, and medical history. Once the subject's basic eligibility has been confirmed, the subject will be scheduled for a screening visit in order to be consented and to continue the screening process.

After signing the informed consent, subjects will finish the screening for study eligibility. All screening evaluations to determine eligibility must be completed within one day prior to study entry. Screening and Pre-Entry evaluations may occur concurrently. All screening activities are consistent with standard of care. Screening includes documentation of diagnosis and medical history.

6.2.1.2. Pre-Entry Day 1

The first day of the subject's visit is Pre-Entry Day 1. Pre-Entry assessments consist of clinical assessment, targeted physical exam, side effect assessment, pregnancy testing if appropriate, and a seizure count.

6.2.2. On-Study/On-Intervention Evaluations

6.2.2.1. Entry Day 1

Subjects will be admitted for a 48 hour inpatient stay for oil administration and monitoring. Entry evaluations will be done within a day of pre-entry and consist of a nutritional assessment, and a blood draw to evaluate hematology and blood chemistry, including a random glucose. We will also obtain blood that is left over from the samples above (if available) or draw an additional 3 mL of blood, if needed, to measure C7 ketones. The collection of this blood for measurement of ketones is optional. A continuous EEG will be completed on subjects over the 48 hour inpatient stay. A peripheral IV will be placed to allow for immediate treatment of breakthrough seizures, should they occur.

6.2.2.2. Day 2

Subjects will be administered C7 starting on the morning of Day 2. Subjects will be given oil at a rate of 45% of their daily caloric intake, divided into 4 doses (breakfast, lunch, dinner, and before bed). A clinical assessment and a side effect assessment will be done. Subjects will be maintained on continuous EEG for the duration of C7 administration. Subjects will receive their final dose in the evening on Day 2. Subjects will have a blood draw to evaluate hematology and blood chemistry. Subjects will undergo a random glucose and beta-hydroxybutyrate level in the morning with their first dose of C7 and at bedtime with their last dose of oil. We will also obtain blood that is left over from the samples above (if available) or draw an additional 3 mL of blood, if needed, to measure C7 ketones. The collection of this blood for measurement of ketones is optional.

6.2.2.3. Day 3 (Intervention Discontinuation Evaluations)

Subjects will remain inpatient until approximately noon on Day 3 to ensure no untoward withdrawal effects from C7. A clinical assessment, a side effect assessment, and a seizure count will be done. Subjects will have a blood draw to evaluate hematology and blood chemistry. Subjects will undergo a random glucose and beta- hydroxybutyrate level in the morning and just prior to discharge. We will also obtain blood that is left over from the samples above (if available) or draw an additional 3 mL of blood, if needed, to measure C7 ketones. The collection of this blood for measurement of ketones is optional. EEG will be stopped just prior to discharge.

6.2.3. Final On-Study Evaluations

Subjects will return for a discontinuation visit on Day 4. Subjects will complete a seizure count, limited side effect assessment (Hague Side Effect Scale), and have non-fasting blood drawn to evaluate hematology and chemistry. We will also obtain blood that is left over from the samples above (if available) or draw an additional 3 mL of blood, if needed, to measure C7 ketones. The collection of this blood for measurement of ketones is optional. Medical history, clinical assessment, targeted physical exam, and VA Toxicity Scale are optional and will be completed

only at PI or sub-Investigator discretion.

This visit will complete their participation, and subjects will be discontinued from the study.

6.2.4. Pregnancy

Subjects will be inpatient for the duration of C7 administration. Subjects receive a pregnancy test prior to study entry, and no pregnancy is anticipated during the 4 day participation.

6.3. Special Instructions and Definitions of Evaluations

6.3.1. Informed Consent

Patients will be brought into a private exam room for the consent process. The coordinator will introduce the study, explain the procedures, the patient rights and responsibilities, and the risks and benefits of the study. [name] or M.D. co-investigator will then discuss any additional questions regarding the study, ensure the patient and family understand the protocol, their responsibilities, and their commitment to the research. Once the [name] or co-investigator is satisfied with the patient and family's understanding and intent to participate in the research, the patient and family will sign the consent form. If the subject is age 10-17 years, the subject must assent to the research study in order to participate. [name] or co-investigator will then sign the consent form documenting that consent was obtained.

The institutional research HIPAA form will also be reviewed with the family and any questions answered. Once the research team feels the subject and family understand the HIPAA form, parent or subject signatures will be obtained.

Once the consent and HIPAA forms have been signed by the subject, parents, and PI or M.D. co-investigator, study procedures may be initiated. The research coordinator will create copies of the consent and HIPAA forms: one copy of each form will be returned to the subject and family, and the original of each document will be filed in the subject's research file for the duration of the subject's participation.

6.3.2. Documentation of Glucose Transporter Type I Deficiency (G1D)

Subjects must provide results of genotyping obtained in a CLIA-certified laboratory identifying the GID mutation.

6.3.3. Medical/Treatment History

Procedure location: Children's Medical Center Rare Brain Disorders Clinic. Facilitators: Principal Investigator or physician co-investigators. All subjects' symptoms, past medical history, and current and past treatments will be obtained using a standardized questionnaire that we have used extensively in metabolic encephalopathies to ensure that symptoms anticipated in G1D are sufficiently characterized (13, 14). For example, seizure frequency (the main indicator of neural dysfunction) is captured by this tool. However, in order to avoid ascertainment bias, a wide range of general questions related to all systems is included. This assessment takes approximately 30 minutes.

6.3.4. Clinical Assessments/Targeted Physical Exam

Procedure location: Children's Medical Center Rare Brain Disorders Clinic and Epilepsy Monitoring Unit. Facilitators: [name] or physician co-investigators. We will utilize a

standardized scoring system previously used by us to assess the clinical findings on examination (13, 14). The tool focuses on the following domains: (a) height, weight, and head circumference; (b) general medical exam; (c) general neurological exam; (d) cranial nerves; (e) stance and gait; (f) involuntary movements; (g) sensation; (h) cerebellar function; (i) muscle bulk, tone and strength; (j) myotatic reflexes, (k) presence of Babinski signs; and (l) other findings. Results of these domains are scored as normal or abnormal and summarized as a total score with 76 being normal. This assessment takes approximately 30 minutes.

6.3.5. Side Effect Assessment

Side effects will be assessed using the Hague Side Effect Scale (15) and the VA Toxicity Scale (16), which are part of the Common Data Elements for NINDS. These scales, between them, measure side effects of anti-epileptic medications, including some gastrointestinal symptoms and systemic effects measured by our safety blood work. Side effects reported by the family but not found on the scales will be noted. These scales take approximately 20 minutes to complete.

6.3.6. Pregnancy testing

Serum or urine pregnancy testing will be done to test for pregnancy. As the majority of our subjects are minors, we do not anticipate the timing will interfere with C7 initiation; however, C7 will not be initiated until the pregnancy results are returned and are confirmed negative.

6.3.7. Nutritional Assessment

The registered dietician will do a complete review of the subject's caloric intake, and work with PI to determine the optimal amount of oil based on the current caloric intake and ketogenic diet ratio. The consult will take approximately 45 minutes.

6.3.8. Seizure count

Subjects and caregivers will be asked to count any seizures they note during the inpatient stay, from prior to oil administration to discharge on Day 3. They will be given a log to record time and description of any visible seizures.

6.3.9. Electroencephalogram

The subjects will undergo continuous EEG recording of brain wave activity for approximately 48 hours during each inpatient stay. The EEG will involve placement of an electrode cap. The subject will be fitted with a cap containing up to 32 electrodes which rest against their scalp, and which allow their brain electrical activity (EEG) to be recorded. An additional electrode will also be placed directly to the skin in the chest. All skin preparation equipment coming into contact with skin is discarded after a single use, and electrodes and caps are cleaned and disinfected immediately after use in accordance with published guidelines. The EEG recording is harmless and painless. Only the application of the electrode cap may involve mild, temporary discomfort. At the end of the session we will remove the cap and electrodes, and help clean the skin if necessary.

6.3.10. Laboratory Evaluations

Hematological and chemical profiles (Comprehensive metabolic panel, lipid panel, , Lactate Whole Blood, Triglycerides, HDL Cholesterol, LDL Cholesterol, Cholesterol , Complete Blood Count, random plasma glucose, and beta-hydroxybutyric acid (a ketone body generated by ketogenic diets) will be measured by standard clinical laboratory methods and compared to normal values established in each laboratory. In addition, subjects will have

blood drawn via IV for random plasma glucose and beta-hydroxybutyric acid levels in the morning and evening on Day 2 and in the morning and before discharge on Day 3. Measurement of C7 ketones will be conducted by a collaborating research laboratory.

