2.2 Supporting Data

There is evidence of beneficial effects of C7 metabolism on the TCA cycle G1D (7). This evidence stems from work in the G1D mouse model via ^{13}C nuclear magnetic resonance (NMR) spectroscopy and mass spectrometry. Open-label treatment using triheptanoin has been pioneered by us in several disorders characterized by impaired anaplerosis (9-12), proving safe, tolerable and efficacious.

The dosing, tolerability, and safety profile of triheptanoin has been documented in other disorders (9-12). Therapeutic response is seen at approximately 35% of the daily caloric needs supplied by C7 oil, and 14 years of experience administering C7 has elicited no serious adverse events. However, side effects of mild stomach upset, nausea, and mild weight gain have been observed. Because C7 oil is a fat, it is possible that subjects will

experience changes in lipid levels, cholesterol, and triglycerides, but these changes have not been observed.

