5. STUDY INTERVENTIONS

5.1. Interventions, Administration, and Duration

5.1.1. Triheptanoin: A triglyceride oil containing three odd-carbon chain-length fatty acids (i.e., a triglyceride of 7-carbon heptanoic acid). Triheptanoin will be taken 4 times (approximately every 6 hours) by mouth for one day. It is dosed 4 times per day, added to ketogenic diet meals (replacing some of the fat in each meal). Subjects will receive supplementation at 45% of daily caloric intake. The oil should be taken with meals, and will be mixed with the rest of the ketogenic diet nutrients for administration.

5.1.2. Fifteen subjects will be enrolled in a 4 day proof of principle trial of triheptanoin. Administration of triheptanoin will be done in the Children's Medical Center Dallas Epilepsy Monitoring Unit.

5.1.3. Subjects will not be required to stop other medications. Subjects will be directed to maintain their usual medications, including rescue seizure medications, as necessary for the course of the study. Subjects may have any clinical medical records transferred back to their referring physician at completion of the study.

5.1.4. Side Effects: 14 years of experience with C7 diet therapy in children and adults (including 14 G1D subjects, and a larger group of patients with fatty acid oxidation defects) has failed to reveal any significant adverse effects (9-12). However, subjects may experience mild gastrointestinal upset or stomach pain, and mild diarrhea. Both of these side effects are usually resolved by lowering the initial dose of oil by one-half and gradually titrating up to the required dose. In addition, subjects who do not follow the recommendations to reduce other fat intake in their diet may experience weight gain. Once oil is discontinued, careful monitoring of fat and calorie intake usually effectively reverses the weight gain. The data indicate no adverse effects on normal metabolism. A side effects questionnaire will be used to track any self-reported side effects. Patient safety information will be updated, if necessary, after completion of this trial.

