7. MANAGEMENT OF ADVERSE EXPERIENCES

Previous experience with C7 oil in different populations has yielded no serious adverse effects. Due to the limited nature of the use of C7 oil, there is no data available on how frequent the following side effects occur, nor if there are differences between normal diet or ketogenic diet.

Breakthrough Seizures: There is the possibility that the administration of C7 oil may result in the subject dropping out of ketosis very quickly, which may lead to breakthrough seizures. Management of these breakthrough seizures will follow standard of care protocol, which could include IV or rectally administered anti-convulsant medications.

Diarrhea: Subjects who experience diarrhea may be instructed to increase the amount of fiber consumed with each meal. In addition, C7 will be administered in a fat free, sugar free food item, such as yogurt or pudding, and subjects are instructed to consume this food over 30 minutes in order to minimize diarrhea. Subjects who cannot tolerate the maximum tolerable dose will be discontinued from the study.

Stomach pain: Subjects who experience stomach pain at any time during the treatment will, under the direct supervision of [name] or M.D. co-investigator, be assessed for severity. If subjects cannot tolerate the recommended dose due to severe stomach pain, they will be discontinued from the study.

Weight gain: Although weight gain is a possible side effect of C7 ingestion, it is a long-term effect, and we do not anticipate significant weight gain over the course of one day.

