9.3. Sample Size and Accrual

In this exploratory pilot study, we will recruit 5 subjects in each of three age groups for a total of 15 subjects. The sample size is not justified because this is an exploratory pilot study that will yield data aimed to enable important future combined or comparative studies. We expect to complete the enrollment of study within 24 months.

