9.5. Data Analyses

Descriptive statistics will be computed for each group and combined age group in this pilot exploratory study. For normally distributed, continuous data, means and standard deviations will be used to describe the demographic and clinical characteristics of the patient population participating in the study. Medians, quartiles, and ranges will be used to describe characteristics of the patient population when the data are continuous, non-normally distributed. For categorical or dichotomous variables, the frequency or the proportion will be reported. The proportion of patients who do not alter EEG in subjects currently receiving the ketogenic diet will be computed along with the corresponding 95% confidence interval using the exact binomial method. The proportion of patients who have stable blood glucose and beta hydroxybutyrate levels during acute and long-term C7 supplementation will be computed using exact binomial method.

Paired t-tests or nonparametric one-sample signed tests will be conducted to test if there were significant changes in EEG and neurological performance indices such as ataxia in G1D patients receiving a normal diet between pre-C7 and post-C7. The objective of this study is to enable future combined or comparative studies to evaluate C7 comparability with the ketogenic diet by evaluating EEG and preservation of glycemia and ketosis. Descriptive statistics will be computed to inform (but not to determine; per the FOA) the sample size needed for a future larger study.

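### Apart from glucose and beta-hydroxybutyrate, the safety panels are read only against laboratory normal values, and no change from the subject's own Day 1 value, or summary of the side-effect scales, is planned

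*Combined protocol and SAP*

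**What the plan says.** The schedule in Section 6.1 marks the side-effect assessment and the haematology/chemistry panel on Days 1, 2, 3 and 4, and C7 on Day 2 only. Under Section 6.2.2 the first dose is on the morning of Day 2, so the Day 1 panel and side-effect record precede C7. On Day 4 there is a "limited side effect assessment (Hague Side Effect Scale"); the VA Toxicity Scale is optional that day.

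Section 6.3.10 lists the panel (metabolic panel, lipids, lactate, blood count, glucose, beta-hydroxybutyrate) and says the results "will be measured by standard clinical laboratory methods and compared to normal values established in each laboratory".

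Section 9.5 promises descriptive statistics by age group and combined, without listing variables. It then says "means and standard deviations will be used to describe the demographic and clinical characteristics of the patient population participating in the study", and gives frequencies or proportions for categorical variables. The analyses it names are for EEG, stability of glucose and beta-hydroxybutyrate, and neurological indices such as ataxia. Adverse effects, the two scales, lipids, lactate, transaminases, creatinine and blood counts are not named.

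Section 7 says of the side effects that "there is no data available on how frequent the following side effects occur, nor if there are differences between normal diet or ketogenic diet". Section 5.1.4 adds: "Patient safety information will be updated, if necessary, after completion of this trial".

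**The concern.** A one-day, single-arm study learns about a C7 effect from the difference between before and after in the same subject. A laboratory reference range answers a different question, namely whether a value is usual for a healthy person.

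Subjects enter on a diet that supplies well over half of calories from fat, and they may be taking anticonvulsants. Some may therefore be outside a range on Day 1. A later out-of-range value in such a subject says nothing by itself about C7, while a rise that stays inside the range is not seen.

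The side-effect scales have the same difficulty. Section 6.3.5 describes them as measuring effects of antiepileptic medication, and Section 5.1.3 keeps subjects on their usual medication, so a symptom recorded after C7 may have been there before.

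At stake is the descriptive safety information from 15 subjects on C7 plus a ketogenic diet. Section 2.1 cites one earlier subject on that combination, and Section 7 says side-effect frequency is unknown.

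**Working it through.** **Inputs.** Section 9.3: "we will recruit 5 subjects in each of three age groups for a total of 15 subjects", that is 3 × 5 = 15, which agrees. The same section says "The sample size is not justified because this is an exploratory pilot study", so there is no power or precision figure to reproduce. No lipid, lactate or enzyme values on the diet and no side-effect rates are given.

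**Step 1: comparator and analysis, item by item.**

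| Item | Days collected | Comparator stated | Analysis named in 9.5 |
|---|---|---|---|
| Glucose, beta-hydroxybutyrate | Panel Days 1–4, plus extra draws Days 2–3 | Normal values (6.3.10; 9.1); previous values (9.2.1.2) | Yes, exact binomial |
| Lipids, lactate, transaminases, creatinine, blood counts | Days 1–4 | Normal values only (6.3.10) | None |
| Hague and VA scales, adverse effects | Days 1–4 (VA optional on Day 4) | None | None by name |

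**Step 2: what a normal-range reading can show.** Classify each subject as in or out of range on Day 1 and again on Day 3.

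- In, then in: reads as normal, whatever the size of the change.
- Out, then out: reads as abnormal, though the abnormality preceded C7.
- In, then out: the informative cell. It is visible only if the two days are linked within subject.

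Tabulating each day separately does not recover that cell. As an illustration, suppose 3 of 15 are out of range on Day 1 and 3 of 15 on Day 3. The number newly out of range can be anything from 0 (the same three subjects) to 3 (three different subjects). As a proportion of 15 that is 0/15, with exact 95% interval 0 to 21.8%, or 3/15, with interval 4.3 to 48.1%. Identical daily counts fit both.

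**Step 3: precision of the proposed summaries.**

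- Counts, by the exact binomial (Clopper-Pearson) method that 9.5 already uses. For zero events the upper limit is 1 − 0.025^(1/n): 21.8% for n = 15 and 52.2% for n = 5. For 1/15 the interval is 0.2 to 32.0%.
- Chance of at least one affected subject, 1 − (1 − p)^n. At assumed true rates of 5%, 10%, 20% and 30%, with n = 15: 53.7%, 79.4%, 96.5% and 99.5%. With n = 5: 22.6%, 41.0%, 67.2% and 83.2%. The rates are assumptions.
- Mean paired change. The 95% half-width is t(0.975, n − 1)/√n in units of the SD of the within-subject change: 2.145/3.873 = 0.55 for n = 15, and 2.776/2.236 = 1.24 for n = 5. That SD is not in the documents, so no half-width in laboratory units can be given.

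**The case against.** The best defence is that Section 9.5 opens with a general promise of descriptive statistics and says frequencies or proportions will be reported for categorical variables. Presence or absence of diarrhoea is such a variable. This has force for the adverse-effect table, where the gap is close to missing detail. It does not supply a definition of new or worsened since Day 1, and it does not change the comparator that 6.3.10 sets for the panels.

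Second, the panel is drawn on Day 1 too, so an existing abnormality would be on file, and Section 10.4.4 has the investigator-sponsor judge causality. That stands for individual subjects. It gives no paired summary for the group and does not pick up in-range changes.

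Third, the study is an exploratory pilot, and its go/no-go rule in Section 9.1 does not use these results. That is correct and limits the weight of the point.

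Fourth, paired changes are not clean. The Day 2 panel has no stated time relative to the doses. Fasting status is stated only for Day 4 (non-fasting), so meals could move triglycerides and lactate. This stands and is carried into the fix.

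Finally, the part of Section 9 between 9.3 and the text on replacing monitoring-committee members is absent from the text available, so a safety summary described there cannot be excluded.

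**Conclusion.** The point holds in limited form. For the panel results other than glucose and beta-hydroxybutyrate, the stated comparator does not fit a within-subject question, although the Day 1 value that would fit is already collected. No summary of these results or of the side-effect scales is named.

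A reader might infer more, and the documents do not support it:

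- That none of the panel is analysed. Glucose and beta-hydroxybutyrate are in the panel, are analysed in 9.5, and are set against previous values in 9.2.1.2.
- That side effects would go unreported. Section 10.4 has adverse experiences collected daily and all adverse effects and abnormal findings recorded, with FDA and IRB reporting for defined categories. Section 10.1 lists a final study report. What is missing is a named group summary, chiefly for mild effects and laboratory changes.
- That a known lipid harm would be misstated. Section 2.2 calls lipid changes possible but not observed so far.

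How often a normal-range reading would mislead cannot be sized, because no baseline values on the diet are given. The precision figures assume all 15 subjects complete; the half-widths also assume roughly normal changes. This is an inexpensive improvement, and it alters neither the primary outcome nor the go/no-go rule.

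**What to change.** 1. In 6.3.10, state that each safety analyte is compared with the subject's own Day 1 value, with normal ranges shown for reference.
2. In 9.5, add for lipids, lactate, transaminases, creatinine and blood counts the within-subject change from Day 1 to Day 3 and to Day 4 with 95% confidence intervals, plus a shift table from in range on Day 1 to out of range later. Present these descriptively, without tests.
3. Use the Day 2 panel only if its time relative to dosing is recorded. Record fasting status at each draw, or state that triglyceride and lactate changes may reflect meals.
4. In 9.5, add the number and proportion of subjects, overall and by age group, with any adverse effect new or worsened since Day 1, with exact binomial intervals. For Day 4, rest this on the Hague scale and recorded adverse effects, since the VA scale is optional that day.

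The cost is a few sentences and two or three small tables; no visit or blood sample is added. The drawback is wide, exploratory intervals without a control group, so a change after C7 cannot be attributed to C7 with confidence. Doses and the discontinuation criteria in Section 8 are not affected.
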